6.7.2 Nivolumab dose modifications and delays

No dose reductions for nivolumab are permitted under this protocol. Nivolumab administration will be delayed for the following:

- 1. Any Grade ≥ 2 non-skin drug-related adverse event, with the following exceptions:
 - a. Grade 2 drug-related fatigue or asymptomatic laboratory abnormalities do not require a treatment delay.
- 2. Any Grade ≥ 3 skin drug-related adverse event.
- 3. Any Grade ≥ 3 drug-related laboratory abnormality with the following exceptions:
 - Grade 3 amylase or lipase abnormalities that are not associated with symptoms or clinical manifestations of pancreatitis do not require a dose delay.
- 4. Dose delay for changes in AST or ALT as follows:
 - a. If a subject has a baseline AST or ALT that is within normal limits, delay dosing for drug-related Grade > 2 toxicity (2 grade shift).
 - b. If a subject has baseline AST or ALT within the Grade 1 toxicity range, delay dosing for drug-related increase to ≥ 8x ULN.
 - c. If a subject has baseline AST or ALT within the Grade 2-3 toxicity range, delay dosing for two-fold drug-related increase in AST or ALT or for AST or ALT values 10x ULN (whichever is lower).
- 5. Any adverse event, laboratory abnormality, or intercurrent illness which, in the judgment of the investigator, warrants delaying the dose of study medication.

See Section 6.8.2 and Appendix 14.5 for guidance on management of toxicity attributed to nivolumab including initiation of immunosuppression for possible immune-related toxicity. Subjects who require delay of nivolumab should be re-evaluated weekly or more frequently if clinically indicated. It is recommended to monitor elevations in AST or ALT at least weekly until levels peak or begin to decline. Nivolumab dosing can be resumed when the following re-treatment criteria are met.

6.7.2.1 Criteria to resume nivolumab dosing after delay for toxicity

Subjects may resume treatment with a study drug after treatment hold for toxicity if the drug-related AE(s) resolve to Grade ≤ 1 or baseline within 6 weeks (42 days), with the following exceptions:

- 1. Subjects may resume treatment in the presence of Grade 2 fatigue.
- 2. Subjects who have not experienced a Grade 3 drug-related skin AE may resume treatment in the presence of Grade 2 skin toxicity.
- 3. Subjects with baseline Grade 1 AST, ALT, or total bilirubin who require dose delays for reasons other than a drug-related hepatic event may resume treatment in the presence of Grade 2 AST, ALT, or total bilirubin.
- 4. Subjects who require dose delays for drug-related elevations in AST, ALT, or total bilirubin may resume treatment when these values have returned to their baseline CTCAE Grade or normal, provided the criteria for unacceptable toxicity requiring permanent discontinuation are not met (Section 6.9).
- 5. Drug-related pulmonary toxicity, diarrhea, or colitis must have resolved to baseline before treatment is resumed.
- 6. Drug-related endocrinopathies adequately controlled with only physiologic hormone replacement are acceptable for resuming treatment.
- 7. A longer treatment delay up to approximately 12 weeks for recovery of treatment-related toxicity in subjects may be permitted in subjects who have demonstrated previous treatment benefit (e.g. radiographic regression and/or clinical improvement such as reduced pain or tumor marker), with approval from Study Chair or designee.

If the criteria to resume treatment are met, the subject should restart treatment at the next scheduled time point per protocol.

6.7.3 Dose delays for reasons other than treatment-related toxicity

Dosing interruptions in either or both drugs are permitted in the case of unrelated medical or surgical events or logistical reasons not related to study therapy (e.g., elective surgery, unrelated medical events, administrative reasons, patient vacation or personal reasons, and/or holidays). Subjects should be placed back on study therapy within approximately 4 weeks (28 days, 1 cycle) of the scheduled interruption if within the first 6 months (6 cycles) of protocol therapy, or within approximately 8 weeks (56 days, 2 cycles) if the delay occurs after the first 6 months (6 cycles) of protocol therapy. Scheduled safety and tumor assessments for all subjects should continue per protocol

even if dosing is delayed.

Longer delays may be permitted on a case-by-case basis if approved in writing by Study Chair.

The reason for interruption should be documented in the patient's study record. Before resuming treatment, patients must demonstrate adequate clinical and laboratory parameters to resume treatment without indication for dose modification or delay according to Section 6.8.

6.8 Supportive care for toxicity

6.8.1 Sorafenib supportive care

Standard supportive care should be provided to all patients according to institutional practice for sorafenib therapy. The following tables provide guidance on supportive care to prevent and/or mitigate toxicity related to sorafenib, to be employed at discretion of treating investigator. The treating investigator may employ different or additional interventions according to institutional practice and clinical judgment.

6.8.1.1 Hand-foot skin reaction (HFSR)

Table 6.8.1.1-1 Guidance on prevention and supportive care for HFSR on sorafenib

Toxicity Grade	Practical Prevention / Management Strategies for HFSR
0 - 1 0 (D 1)	 Maintain frequent contact with trial physician to ensure early diagnosis of HFSR. Practical prevention strategies
Grade 0 (Preventive strategies)	 Subjects should avoid hot water, tight clothing, or activities that can cause friction on the skin. Moisturizing cream should be applied frequently.
	 Padded gloves and open shoes with padded soles should be worn to relieve pressure points.
Grade 1	Continue preventive strategies and in addition:
Any occurrence	Soak hands and feet in cool water.Apply petroleum jelly to moist skin.
Grade 2 Any occurrence or Grade 3 Any occurrence	Continue supportive/management measures and add analgesic(s) for pain.

6.8.1.2 **Diarrhea**

Diarrhea is a common side effect of sorafenib. The preventive and supportive care strategies for diarrhea should be consistent with local standard of care on sorafenib (e.g., anti-diarrheals, optimized hydration status for diarrhea, dietary modifications).

6.8.1.3 Treatment-emergent hypertension

Hypertension is a known and potentially serious AE associated with sorafenib treatment. Subjects will undergo brief physical examinations, including blood pressure monitoring, approximately every other week per Section 7.1. Blood pressure measurements that are out of the normal range must be reported to the treating

physician. Blood pressure measurements considered out of the normal range are diastolic pressure > 90 mm Hg and/or systolic pressure > 140 mm Hg.

The choice of anti-hypertensive medication to be used in cases of treatment-emergent hypertension will be at the investigator's discretion and based on site-specific treatment guidelines as applicable. All anti-hypertensive medications used for the management of treatment-emergent hypertension should be recorded in the subject's records.

6.8.2 Nivolumab supportive care

6.8.2.1 Immune-related adverse events (irAE) on nivolumab

For potential immune-related adverse events (irAE) attributed to nivolumab, immunosuppressive therapy should be promptly initiated at discretion of treating investigator. General guidelines for immunosuppressive therapy are provided below. Specific guidance for common irAE are provided in Appendix 14.6.

Note that several courses of steroid tapering may be necessary as symptoms may worsen when the steroid dose is decreased. For each disorder, attempts should be made to rule out other causes such as metastatic disease or bacterial or viral infection, which might require additional supportive care. These treatment guidelines are intended to be applied when the investigator determines the events to be related to nivolumab.

Suggested steroid regimens include:

- 1. Systemic steroids equivalent to prednisone 1-2 mg/kg/day for severe immune-related toxicity requiring immunosuppressive therapy.
- 2. Oral prednisone 0.5 mg/kg/day or other equivalent steroid regimen for mild-moderate immune-related toxicity requiring immunosuppressive therapy.
- 3. Topical corticosteroids for mild-moderate dermatitis.
- 4. Corticosteroid eye drops for ocular immune-related toxicity.

Supportive care on prolonged steroid therapy including blood pressure and blood glucose monitoring, gastroprotection with proton pump inhibition, and antibacterial prophylaxis (e.g. trimethoprim-sulfamethoxazole prophylactic doses) should be employed at discretion of treating investigator according to institutional standards.

Once symptoms resolve or return to Grade 1/baseline, initiate slow steroid taper over at least 4 weeks, with close monitoring. It may be necessary to perform conditional procedures such as bronchoscopy, endoscopy, or skin photography as part of evaluation of the event.

6.8.2.2 Infusion reactions during nivolumab infusion

Since nivolumab contains only human immunoglobulin protein sequences, it is unlikely to be immunogenic and induce infusion or hypersensitivity reactions. However, if such a reaction were to occur, it might manifest with fever, chills, rigors, headache, rash,

pruritus, arthralgias, hypo- or hypertension, bronchospasm, or other symptoms. Infusion reactions should be graded according to NCI CTCAE (version 4.03) guidelines.

Treatment recommendations are provided below and may be modified based on local treatment standards and guidelines as appropriate:

- 1. For Grade 1 symptoms: (Mild reaction; infusion interruption not indicated; intervention not indicated)
 - o Remain at bedside and monitor subject until recovery from symptoms.
 - For future infusions, the following prophylactic premedications are recommended: Diphenhydramine 50 mg (or equivalent) PO and acetaminophen 325 to 1000 mg PO at least 30 minutes before additional nivolumab administrations.
- 2. For Grade 2 symptoms: (Moderate reaction requires therapy or infusion interruption but responds promptly to symptomatic treatment [eg, antihistamines, non-steroidal anti-inflammatory drugs, narcotics, corticosteroids, bronchodilators, IV fluids]; prophylactic medications indicated for ≤ 24 hours).
 - Stop the nivolumab infusion, begin an IV infusion of normal saline, and treat the subject with diphenhydramine 50 mg IV (or equivalent) and acetaminophen 325 to 1000 mg PO; remain at bedside and monitor subject until resolution of symptoms. Corticosteroid or bronchodilator therapy may also be administered as appropriate. If the infusion is interrupted, then restart the infusion at 50% of the original infusion rate when symptoms resolve; if no further complications ensue after 30 minutes, the rate may be increased to 100% of the original infusion rate. The amount of study drug infused must be recorded on the electronic case report form (eCRF). Monitor subject closely. If symptoms recur, then no further nivolumab will be administered at that visit.
 - For future infusions, the following prophylactic premedications are recommended: Diphenhydramine 50 mg PO (or equivalent) and acetaminophen 325 to 1000 mg PO should be administered at least 30 minutes before additional nivolumab administrations. If necessary, corticosteroids (recommended dose: up to 25 mg of IV hydrocortisone or equivalent) may be used.
- 3. For Grade 3 or Grade 4 symptoms: (Severe reaction, Grade 3: prolonged [i.e., not rapidly responsive to symptomatic medication and/or brief interruption of infusion]; recurrence of symptoms following initial improvement; hospitalization indicated for other clinical sequelae [e.g., renal impairment, pulmonary infiltrates]). Grade 4: (life threatening; presser or ventilator support indicated).
 - Immediately discontinue infusion of nivolumab. Begin an IV infusion of normal saline, and treat the subject as follows: Recommend bronchodilators, epinephrine 0.2 to 1 mg of a 1:1,000 solution for subcutaneous administration or 0.1 to 0.25 mg of a 1:10,000 solution injected slowly for IV administration, and/or diphenhydramine 50 mg IV with methylprednisolone 100 mg IV (or equivalent), as needed.

 Subject should be monitored until the investigator is comfortable that the symptoms will not recur.

- Nivolumab will be permanently discontinued.
- Investigators should follow their institutional guidelines for the treatment of anaphylaxis. Remain at bedside and monitor subject until recovery from symptoms.
- 4. In the case of late-occurring hypersensitivity symptoms (e.g., appearance of a localized or generalized pruritus within 1 week after treatment), symptomatic treatment may be given (e.g., oral antihistamine, or corticosteroids).

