6.2.3.3 DLT exceptions

The following AE will not be considered DLT:

- 1. Asymptomatic Grade 3 non-hepatic laboratory values, with the following specifications:
 - a. Asymptomatic Grade 3 laboratory values are only considered DLT if determined treatment-related and clinically significant (e.g. requiring therapeutic intervention)
 - b. Liver function test abnormalities will be determined DLT according to DLT definitions in Section 6.2.3.

- 2. Grade 3 hypertension that resolves to ≤140/90 within 7 days of adjustment or addition of oral blood pressure medication(s)
- 3. Grade 3 HFSR attributed to sorafenib
- 4. Grade 3 infusion reactions which resolve within 6 hours of supportive therapy are not considered DLT but require nivolumab discontinuation (see Section 6.9)
- 5. Grade 3 fatigue
- 6. Toxicity attributed to hepatocellular carcinoma (e.g. AE due to mass effect, obstruction, or pain caused by tumor growth or new lesions)

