6.9.2 Unacceptable toxicity related to nivolumab

Treatment with nivolumab should be permanently discontinued for the following toxicities attributed to nivolumab therapy:

- 1. Any Grade ≥ 2 ophthalmologic irAE such as uveitis causing eye pain or reduction of visual acuity that does not improve to Grade ≤ 1 severity within 14 days of starting topical therapy or requires systemic treatment
- 2. Any Grade ≥ 3 non-skin, drug-related adverse event that does not downgrade to Grade ≤ 2 within 7 days with optimal medical management including systemic corticosteroids and/or hormone replacement and/or does not downgrade to ≤ Grade 1 or baseline within 14 days, with the following exceptions:
 - a. Any Grade ≥ 2 pneumonitis irAE that does not improve to ≤ Grade 1 within 7 days of initiation of maximal supportive care requires discontinuation
 - Any event of Grade ≥ 3 drug-related uveitis, bronchospasm, pneumonia or pneumonitis, hypersensitivity reaction, or infusion reaction regardless of duration requires discontinuation
 - c. Grade 3 drug-related endocrinopathies adequately controlled with only physiologic hormone replacement do not require discontinuation
 - d. Asymptomatic/uncomplicated Grade 3 drug-related laboratory abnormalities do not require treatment discontinuation
- 3. Hepatotoxicity as evidenced by the following lab values requires discontinuation:

- a. AST or ALT > 8 x ULN for > 2 weeks, irrespective of baseline
- b. AST or ALT > 15 x ULN irrespective of baseline or duration
- c. Total bilirubin > 5 x ULN, irrespective of baseline or duration
- 4. Any Grade 4 drug-related adverse event or laboratory abnormality requires discontinuation, except for the following events which do not require discontinuation:
 - a. Grade 4 neutropenia < 7 days
 - b. Grade 4 lymphopenia or leukopenia
 - Isolated Grade 4 amylase or lipase abnormalities that are not associated with symptoms or clinical manifestations of pancreatitis including no evidence of pancreatitis on CT or MRI imaging
 - d. Isolated Grade 4 electrolyte imbalances or abnormalities that are not associated with clinical sequelae and are corrected with supplementation and appropriate management within 7 days of their onset
 - e. Grade 4 drug-related endocrinopathies adequately controlled with only physiologic hormone replacement do not require discontinuation
- 5. Any dosing delay for treatment-related toxicity lasting > 6 weeks (42 days) with the following exceptions:

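### Section 6.8.2.2 item 2 keeps a recurrent infusion reaction in the Grade 2 branch, although item 3 defines it as Grade 3 and requires nivolumab to stop permanently

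*Combined protocol and SAP*

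**What the plan says.** Section 6.8.2.2 sets the grading rule for nivolumab infusion reactions: "Infusion reactions should be graded according to NCI CTCAE (version 4.03) guidelines". It then gives separate instructions by grade.

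- **Item 2 (Grade 2), acute management.** Stop the infusion and treat. If it was interrupted, "restart the infusion at 50% of the original infusion rate when symptoms resolve". Then: "If symptoms recur, then no further nivolumab will be administered at that visit". The amount infused must be entered on the eCRF.
- **Item 2, later infusions.** Antihistamine and acetaminophen "should be administered at least 30 minutes before additional nivolumab administrations". The bullet makes no distinction between reactions that recurred and reactions that did not.
- **Item 3 (Grade 3 or 4).** The Grade 3 description includes "recurrence of symptoms following initial improvement". The action is: "Nivolumab will be permanently discontinued".

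Three other places bear on the same event:

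- Section 6.9.2 item 2b, for drug-related events of Grade 3 or higher: "hypersensitivity reaction, or infusion reaction regardless of duration requires discontinuation".
- Section 6.2.3.3 item 4: "Grade 3 infusion reactions which resolve within 6 hours of supportive therapy are not considered DLT but require nivolumab discontinuation".
- Section 6.5.1.2 recommends premedication for retreatment only where the earlier reaction was below Grade 3 and the patient has been judged eligible for retreatment.

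**The concern.** A patient whose symptoms return after a restart falls under two instructions at once. Item 2 treats the event as a Grade 2 reaction and limits the consequence to the current visit. Item 3 calls the same event Grade 3 and ends nivolumab. Staff managing a Grade 2 reaction will be reading item 2, and nothing there tells them that the grade has changed.

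The grade decides four things:

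- **Further dosing.** At Grade 3, nivolumab stops, and under Section 6.9 sorafenib stops with it. Left at Grade 2, the patient could be premedicated and given nivolumab again.
- **Acute care.** Item 3 lists stronger measures and monitoring until the investigator no longer expects symptoms to return.
- **Safety reporting.** A Grade 3 or 4 infusion reaction is an SAE by definition (Section 7.4.1.2, criterion 6) and goes to Bayer within one business day (Section 7.4.2).
- **The Part 2 primary endpoint.** Section 8.2.1.2 uses the rate of related AEs of Grade 3 or higher.

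**Working it through.** The plan gives no figure to reproduce here. The main check is textual, with short arithmetic for the size.

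**1. Does recurrence after a restart meet the Grade 3 description?** Item 2 allows a restart only after symptoms have resolved. Resolution is at least an improvement. Symptoms that return after the restart therefore follow an initial improvement, which is item 3's Grade 3 criterion.

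**2. Dispositions side by side.**

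| Place | Grade given to the event | Consequence for nivolumab |
|---|---|---|
| 6.8.2.2 item 2 | Stays under the Grade 2 heading | None for the rest of the visit; premedication bullet for later infusions |
| 6.8.2.2 item 3 | Grade 3 | Permanent stop |
| 6.9.2 item 2b | Applies at Grade 3 or higher | Permanent stop, whatever the duration |
| 6.2.3.3 item 4 | Applies at Grade 3 | Stop, even when the event is not a DLT |

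**3. Do other rules catch it?** The Grade 3 limit in Section 6.5.1.2 works only after the event has been regraded. An event left at Grade 2 passes that limit. Once it has resolved to Grade 1 or less, it also meets the general resumption criterion in Section 6.7.2.1.

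**4. Time for the weekly check.** Appendix 11, Section 3.1 has the Site Committee review the AEs entered in OnCore every week, including their grade. Section 6.5.1.1 gives the dosing intervals:

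- 14-day schedule: minimum 12 days; latest without a delay 14 + 3 = 17 days.
- 28-day schedule (Part 2 option on or after C4D1): minimum 24 days; latest without a delay 28 + 6 = 34 days.

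Weekly meetings before the next dose are at least floor(12/7) = 1 on the 14-day schedule and floor(24/7) = 3 on the 28-day schedule. The review may therefore catch an error first, provided the AE has been entered by then. Section 9.6 sets no fixed deadline for completing the forms. The AE fields listed in Section 7.4 include grade but not recurrence.

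**5. Effect on the Part 2 primary rate.** One patient moved from Grade 2 to Grade 3 changes the rate by 0 if that patient already has another related AE of Grade 3 or higher, and otherwise by 1/n. Section 8.2.1.2 plans for n = 12 and tabulates smaller cohorts in case accrual closes early:

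| n | 1/n, percentage points |
|---|---|
| 12 | 8.3 |
| 10 | 10.0 |
| 8 | 12.5 |
| 6 | 16.7 |

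**6. Frequency.** The documents give no rate of infusion reactions or of recurrence. Section 6.8.2.2 describes such reactions as unlikely.

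**The case against.** The strongest reply is that the operative rules already agree. CTCAE grading is required. Item 3 comes directly after item 2 and states the Grade 3 criterion. Sections 6.9.2 and 6.2.3.3 give the same outcome, and Section 6.5.1.2 asks for a separate judgement of eligibility before retreatment. On this reading the visit-limited sentence is only the immediate bedside step. The premedication bullet lapses by its own heading once the event is Grade 3, and all that is missing is a cross-reference.

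Much of this stands. A reader might infer that item 2 authorises rechallenge after recurrence. It does not: the sentence is compatible with a permanent stop, and no other section permits another dose once the event is Grade 3. What the reply does not remove is that every one of these protections depends on a regrade, and item 2 does not prompt one. Its limit to the visit, followed by an unqualified bullet on later infusions, leaves the event looking like Grade 2. The clause allowing local modification of the recommendations in 6.8.2.2 does not settle the matter either, because 6.9.2 has no such clause.

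The reply is also right about safeguards. Besides the weekly review, the investigator approves the CRFs (Section 9.6), AE monitoring is scheduled at each infusion visit, and item 2 requires the amount infused to be recorded. An infusion abandoned after recurrence would normally show as a partial dose. That is a useful flag, but it does not by itself show that symptoms recurred.

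**Conclusion.** The conflict is in the current text: one event receives two dispositions in a bedside safety instruction. It is a low-frequency safety clarification, worth making because the correction is short and the instruction concerns re-exposure to a drug that the protocol says must stop.

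The number of patients affected is probably very small and cannot be estimated from the documents. One regraded patient changes the Part 2 primary rate by 0 to 1/n, which is up to 8.3 points at n = 12 and up to 16.7 at n = 6.

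Two stronger readings are tempting, and the documents support neither. A reader might infer that affected patients would go on to receive most of their planned infusions. That would require the misgrading to escape the weekly review and every other check, and nothing in the documents gives a probability for it. A reader might also infer that the primary safety result is unreliable. With no event rate, the documents support only the per-patient bound above.

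The conclusion assumes that a return of symptoms after a restart is recurrence in the sense of item 3, which follows from the restart condition.

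**What to change.** In Section 6.8.2.2 item 2, replace the recurrence sentence with: *If symptoms recur after initial improvement, stop the infusion, regrade as Grade 3 and follow item 3 and Section 6.9.2 (permanent discontinuation).* Limit the item 2 premedication bullet to reactions that did not recur.

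Check infusion reactions already recorded as Grade 2 for recurrence, using the amount infused on the eCRF as a flag and confirming against source. SAE and primary-endpoint classification then follow from Sections 7.4.1.2 and 8.2.1.2 without further text.

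The cost is one sentence and one qualifier in an amendment or clarification memo, plus the record check. The downside is possibly a few more permanent discontinuations, each ending both drugs under Section 6.9 in patients with few options. The protocol already requires that for Grade 3 infusion reactions. Accrual was due to close on 30 April 2022, so the change mainly serves patients still receiving infusions and the final grading.
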